6.6.3 Secondary Efficacy Analyses

The secondary efficacy endpoints are identified in Section 2.1.2.

Similar hypotheses as for the primary efficacy endpoint will be tested for the secondary continuous efficacy endpoints.

Categorical endpoints, such as CGI-C and the proportion of progressors, will be analyzed by means of logistic regression and will include treatment (categorical), CAG repeat length, and CAP score as covariates.

Methods for controlling type I error in the testing of the secondary endpoints will be described in the SAP.

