Note: The primary efficacy endpoint for the U.S. FDA will be change from baseline in the TFC score at Week 101. TFC will be analyzed the same way as the cUHDRS.

The primary efficacy analysis for this study will compare each active treatment arm, RO7234292 Q8W and RO7234292 Q16W, against the placebo arm. To account for the multiple comparison, an appropriate procedure will be used to maintain the overall two-sided type I error at 5% (details will be given in the SAP).

The analysis of the primary endpoint will be performed by means of analysis of covariance (ANCOVA). The model will include the corresponding endpoint baseline score, CAG repeat length, baseline CAP score, and treatment as covariates; the final list of covariates will be defined in the SAP. On the basis of this analysis, least squares mean for the treatment differences at Week 101 and corresponding 95% CIs will be derived.

The robustness of the primary method of estimation described above may be explored by alternative sensitivity estimators based on varying assumptions underlying the multiple imputation strategy. These sensitivity analyses will be described in the SAP.

Determination of Sample Size

The planned sample size is adequate to capture meaningful clinical decline on both the TFC and cUHDRS and was estimated on the basis of data available from non-interventional studies (TRACK-HD, COHORT, ENROLL-HD) and a randomized placebo-controlled study (2CARE). Based on these data, using the anticipated trial population, a meta-analysis for the change from baseline at 24 months in TFC score suggested a natural decline of 1.36 points and a corresponding pooled standard deviation of 1.78. A conservative treatment discontinuation rate at Week 101 for patients receiving placebo or active is assumed to be 20% and 15%, respectively. Using these assumptions, the simulation described in the protocol was performed to estimate the sample size.

It was estimated that 267 patients per arm will provide approximately 80% power, at a two-sided $\alpha = 0.025$ level, to detect a 40% slowing of clinical decline for RO7234292 as compared with placebo at 101 weeks. This treatment effect translates into an expected average decline of ~ 0.82 points at 101 weeks for the RO7234292 arms. The minimal detectable difference with these assumptions is ~ 0.38 points.

Optional Interim Analyses

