4.5.9.9 Clinical Global Impression, Severity and Change Scales

The CGI-S is a single-item measure of current global severity and is completed by the clinician at specified clinic visits. The CGI-S is assessed using an 11-point numeric rating scale (NRS), where higher scores indicate greater severity. The CGI-S can be completed in approximately 2 minutes.

The CGI-C is a single-item measure of change in global status (since starting the study) and is completed by the clinician at specified postbaseline visits. The CGI-C has seven response options: "very much worse," "much worse," "minimally worse," "no change," "minimally improved," "much improved," and "very much improved." The CGI-C can be completed in approximately 2 minutes. To assess the relevance of this change, a follow-up question with dichotomous response options ("yes" or "no") asks if the change has had a meaningful impact on the patient's well-being.

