6.6.2 Primary Efficacy Analysis

The primary efficacy endpoint is the change from baseline in cUHDRS score at Week 101. This is defined as the attribute "variable" of the primary estimand in Section 6.6.1.

Note: The primary efficacy endpoint for the U.S. FDA will be change from baseline in the TFC score at Week 101. TFC will be analyzed the same way as the cUHDRS.

The primary efficacy analysis for this study will compare each active treatment arm, RO7234292 Q8W and RO7234292 Q16W, against the placebo arm.

To account for the multiple comparison, an appropriate procedure will be used to maintain the overall two-sided type I error at 5% (details will be given in the SAP).

The analysis of the primary endpoint will be performed by means of analysis of covariance (ANCOVA). The model will include the corresponding endpoint baseline score, CAG repeat length, baseline CAP score (defined in Section 4.1.1), and treatment as covariates. On the basis of this analysis, least squares mean for the treatment differences at Week 101 and corresponding 95% CIs will be derived.

The robustness of the primary method of estimation described above may be explored by alternative sensitivity estimators based on varying assumptions underlying the multiple imputation strategy. These sensitivity analyses will be described in the SAP.

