6.6.4 Subgroup Analyses

The results of selected efficacy variables will be summarized within subgroups using descriptive statistics. The following variables will be used to define subgroups:

- Sex (male vs. female)
- Age at baseline (< 45 vs. \geq 45 years)
- CAG repeat length (< 43 vs. \geq 43)
- Stage at baseline (I, II, III)
 - Stage III will be considered only if there are enough patients.

Additional exploratory analyses of efficacy results may be performed using an ANCOVA model, similar to the primary analysis, based on change from baseline for the variable of interest, with baseline score (not for analysis by baseline stage), CAP score, CAG repeat length (not for analysis by CAG repeat length), treatment, subgroup, and treatment-by-subgroup interaction as covariates.

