6.10 BIOMARKER ANALYSES

The biomarker endpoints are described in Section [2.5](#).

A mixed-effects model repeat measurement model will be used to model the change in each primary and secondary biomarker endpoint, adjusting for the baseline endpoint, CAG repeat length, CAP score, treatment, visit, and treatment-by-visit interaction (the final list of covariates and details of the model will be specified in the SAP).

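### The logistic models for the two progressor endpoints leave out the baseline score that the ANCOVA of the same scales includes, giving up a modest and uncertain amount of power

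*Protocol*

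**What the plan says.** Section 2.1.2 lists two secondary endpoints that cut a change score at a fixed value: TFC down by 1 point or more, and cUHDRS down by 1.2 points or more, both at Week 101. Section 6.6.3 states that categorical endpoints, these included, "will be analyzed by means of logistic regression and will include treatment (categorical), CAG repeat length, and CAP score as covariates".

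For the continuous change on the same two scales, Section 6.6.2 specifies an ANCOVA: "The model will include the corresponding endpoint baseline score, CAG repeat length, baseline CAP score (defined in Section 4.1.1), and treatment as covariates". The biomarker model in Section 6.10 also carries the baseline value, "adjusting for the baseline endpoint, CAG repeat length, CAP score, treatment, visit, and treatment-by-visit interaction".

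The synopsis says of the primary ANCOVA that "the final list of covariates will be defined in the SAP", and Section 6.10 has a similar clause. Section 6.6.3 has none for the logistic models. What it hands over is narrower: "Methods for controlling type I error in the testing of the secondary endpoints will be described in the SAP". The opening of Section 6 does leave the details of all planned analyses to the SAP.

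**The concern.** Whether a patient crosses a fixed threshold of decline can depend on where that patient starts. Entry is set by the Independence Scale and CAP score without a TFC range (Section 4.1.1), and Section 6.6.4 allows for Stages I to III, so starting values may vary widely. CAG repeat length and CAP score may not capture that variation fully.

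If baseline predicts decline beyond CAG and CAP, omitting it wastes information already collected. It also leaves the responder comparison exposed to chance baseline imbalance that the ANCOVA removes. At stake is some power for two secondary endpoints in each of the two testing chains of Section 6.3, and consistency between the continuous and dichotomised analyses of one scale.

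**Working it through.** **1. The plan's own figure.** Inputs from Section 6.2: placebo decline 1.36, active decline 0.82 (difference 0.54), SD 1.78, 267 per arm, two-sided alpha 0.025, discontinuation 20% and 15%.

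- Re-running the described simulation (two visits, stated missingness, 20 imputations, t-test with Rubin pooling; 3,000 replicates) gives 80.0% power, against about 80% stated.
- Minimal detectable difference: 267 × 0.80 = 213.6 and 267 × 0.85 = 226.95, so 2.2414 × 1.78 × √(1/213.6 + 1/226.95) = 0.380, against about 0.38 stated.

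The sizing reproduces. The protocol states no power for a responder endpoint.

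**2. Implied TFC responder rates**, under the same normal model:

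- Placebo: Φ((1.36 − 1)/1.78) = Φ(0.202) = 58.0%
- Active: Φ((0.82 − 1)/1.78) = Φ(−0.101) = 46.0%

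A two-proportion test with 267 per arm at alpha 0.025 then has 70.8% power without covariates.

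**3. Logistic model with and without baseline.** Simulated with 4,000 replicates per setting and no missing data. Both models contain treatment and CAP; the second adds the baseline score. CAG was not simulated separately. The documents give none of the correlations needed, so all are assumptions: baseline-change from 0 to 0.5, CAP-change 0.1, CAP-baseline 0 or 0.4.

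| Baseline-change correlation | Power without / with baseline (CAP-baseline 0) | Power without / with baseline (CAP-baseline 0.4) | Variance of standardised risk difference, with ÷ without (CAP-baseline 0) | SE of conditional log odds ratio, without → with (CAP-baseline 0) |
|---|---|---|---|---|
| 0 | 70.2 / 70.7% | 70.8 / 70.6% | 1.00 | 0.176 → 0.176 |
| 0.1 | 70.8 / 71.4% | 71.0 / 70.9% | 0.99 | 0.176 → 0.177 |
| 0.2 | 70.4 / 72.0% | 70.6 / 71.1% | 0.97 | 0.176 → 0.179 |
| 0.3 | 71.7 / 75.0% | 71.0 / 73.0% | 0.95 | 0.176 → 0.182 |
| 0.4 | 72.4 / 76.7% | 71.2 / 75.9% | 0.91 | 0.176 → 0.187 |
| 0.5 | 71.4 / 79.8% | 70.8 / 79.4% | 0.84 | 0.176 → 0.194 |

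The Monte Carlo SE of one power figure is √(0.7 × 0.3/4,000), about 0.7 points, so differences in the first rows are indistinguishable from zero.

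**4. Sensitivity.** A run without CAP in either model (3,000 replicates) gave changes of −1.0, −0.8, 0.2, 1.6, 3.4 and 7.6 points over the same correlations. Moving the cut to 0.5, to mimic an integer TFC score, gave rates of 68.6% and 57.1% and changes of −0.1, −0.1, 1.0, 2.7, 4.4 and 8.4 points. The pattern is the same.

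**5. Where the gain comes from.** In the run without CAP (cut at 1 point, correlation 0.5), the mean log odds ratio moves from −0.489 to −0.587 and its SE from 0.175 to 0.192. The ratio goes from 0.489/0.175 = 2.8 to 0.587/0.192 = 3.1. The estimate grows faster than its SE: power rises although the odds ratio itself is not estimated more tightly. On the risk-difference scale, variance does fall.

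**The case against.** The strongest reply is that this belongs to the SAP, which is not shown and may already include baseline. Section 6 opens by leaving details to it, and nothing is contradicted, since Sections 6.6.2 and 6.6.3 concern different endpoint types. That stands as a caution. It does not remove the point: Section 6.6.3 names a specific list without baseline, and an analysis that follows it as written is the less efficient one.

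Several stronger readings are tempting, and the documents do not support them:

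- **That the responder tests are biased or invalid.** They are not. Randomisation protects the comparison; type I error, the primary analysis and the sample size are untouched.
- **That power is lost on four tests (two endpoints, two arms).** Under Section 6.3 each test is reached only if the preceding one in its chain is significant, and the order is left to the SAP. Only TFC was simulated; no figure exists for cUHDRS.
- **That precision is lost on the odds ratio.** The SE of the conditional log odds ratio rises with adjustment. The gain is in power and in the standardised risk difference.
- **That CGI-C shares the fault.** Section 4.5.9.9 says CGI-C "is completed by the clinician at specified postbaseline visits", so it has no baseline of its own. CGI-S is a different instrument, and no gain from adding it is shown.
- **That the stage-subgroup ANCOVA in Section 6.6.4 shares it.** That model is optional and exploratory. Its exclusion, "with baseline score (not for analysis by baseline stage", looks deliberate: stage is a banding of TFC, and the same sentence drops CAG from the CAG subgroup.

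It is also fair to say that dosing stopped on unfavourable trends (Section 1.3), so power to detect a 40% slowing now has limited practical weight. A consistent Week 101 comparison remains useful.

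**Conclusion.** The omission is real and confined to the two progressor models. It is a low-priority efficiency and consistency improvement, not an error that threatens a conclusion.

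For the TFC endpoint the gain forgone is about 0 to 2 points of power at a correlation of 0.2 or below, 2 to 5 points at 0.3 to 0.4, and 8 to 9 points at 0.5. The variance of the standardised risk difference is lower by 0% to 16% over that range. These figures assume normal change scores, complete data and the Section 6.2 effect. They hinge on a baseline-change correlation that the protocol does not report; if it is small, almost nothing is lost.

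**What to change.** In Section 6.6.3 and the SAP:

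- Add baseline TFC to the model for the TFC progressor endpoint, and baseline cUHDRS to the model for the cUHDRS progressor endpoint.
- Name the effect measure, for example the standardised risk difference, because the conditional odds ratio changes with the covariates.
- Report the model as now written as a sensitivity analysis.

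The data cost is nil: TFC, TMS, SDMT and SWR are all collected at baseline (Appendices 1a, 2 and 3). There are two small costs. The conditional odds ratio takes on a different meaning from the one under the present model. And because Sections 3.1.2 and 4.2 have the sponsor unblinded following the decision to stop study treatment, effective 22 March 2021, the change must be dated and documented so that readers can see when it was made relative to access to treatment codes. If the SAP already adjusts for baseline, only the protocol text needs aligning.

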6.6.4 Subgroup Analyses

The results of selected efficacy variables will be summarized within subgroups using descriptive statistics. The following variables will be used to define subgroups:

- Sex (male vs. female)
- Age at baseline (< 45 vs. \geq 45 years)
- CAG repeat length (< 43 vs. \geq 43)
- Stage at baseline (I, II, III)
 - Stage III will be considered only if there are enough patients.

Additional exploratory analyses of efficacy results may be performed using an ANCOVA model, similar to the primary analysis, based on change from baseline for the variable of interest, with baseline score (not for analysis by baseline stage), CAP score, CAG repeat length (not for analysis by CAG repeat length), treatment, subgroup, and treatment-by-subgroup interaction as covariates.

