Individuals with HD can be categorized as having either premanifest disease (diagnosed prior to motor onset) or manifest disease (diagnosed on the basis of motor onset). The premanifest disease period can be subdivided into presymptomatic and prodromal periods. During the presymptomatic period, from birth to young adulthood, individuals are not clinically distinguishable from controls. During the prodromal period, which can last many years before threshold clinical motor diagnosis, subtle motor changes and variable cognitive and behavioral changes appear but are not sufficient to make the clinical diagnosis of HD.

The manifest disease period can be subdivided into five stages based on functional capacity (Ross et al. 2014). Stage 1 represents the highest level of capacity and is characterized by mild or no incapacity in terms of independence in daily activities.

Stage 5 represents severe disability and dependence on full-time care (Shoulson and Fahn 1979). The five clinical stages are defined by the score on the UHDRS Total Functional Capacity (TFC) Scale, with Stage 1 corresponding to TFC scores of 11–13, Stage 2 to scores of 7–10, Stage 3 to scores of 3–6, Stage 4 to scores of 1–2, and Stage 5 to a score of 0 (Shoulson et al. 1979).

Currently approved treatments aim to reduce the burden of symptoms, maximize function, and improve the patient's quality of life (Nance et al. 2011). Tetrabenazine and deutetrabenazine target abnormal involuntary movements (i.e., chorea) associated with HD, and these symptomatic therapies have a challenging benefit–risk profile. These drugs have been linked to many significant adverse events, including parkinsonism, akathisia, sedation, and depression and suicidal thoughts. They are contraindicated in patients who are actively suicidal and in patients with untreated or inadequately treated depression. Additionally, they may prolong the corrected QT interval (QTc), and caution is advised when used in combination with other drugs or medical conditions that potentially prolong the QTc.

Other medications are utilized in HD to address particular symptoms, such as antidepressants (for depression, agitation, irritability), anticonvulsants (for irritability, impulsive behavior), anxiolytics (for anxiety), cognitive-enhancing agents (for cognitive disturbances), and neuroleptics (for chorea) (Paulson and Albin 2011).

To date, there are no approved treatments able to slow or stop the clinical progression of HD.

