4.5.9.1 Composite Unified Huntington's Disease Rating Scale

The cUHDRS is a composite motor, cognitive, and global functional clinical outcome measure in patients with HD comprised of an equally weighted sum of Z scores of the TFC, the TMS, the SDMT, and the SWR scores from the UHDRS (Huntington Study Group 1996). It is a multidomain measure of clinical decline that tracks underlying progressive brain changes and is related to changes in daily functional ability (Schobel et al. 2017).

The formula for cUHDRS scoring was originally developed for use in HD Stages 1 and 2 (TFC 7–13) but has since been updated to encompass early HD Stage 3. This led to an update to the reference population (using ENROLL-HD data) from TFC=7–13 to TFC=5–13 (in both cases, a lower age cutoff of 20 years was used to limit the number of individuals included with juvenile-onset HD). The cUHDRS is scored using the following formula:

$$cUHDRS = \left(\frac{TFC - 8.8}{2.8} \right) - \left(\frac{TMS - 34.4}{17.4} \right) + \left(\frac{SDMT - 25.2}{12.4} \right) + \left(\frac{SWRT - 58}{21.2} \right) + 10.0$$

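### The optional subgroup ANCOVA drops the baseline score by stage and continuous CAG length by CAG group, losing a little precision for no stated reason

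*Protocol*

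**What the plan says.** Section 6.6.4 makes description the main subgroup output: "The results of selected efficacy variables will be summarized within subgroups using descriptive statistics". It then adds an optional model: "Additional exploratory analyses of efficacy results may be performed using an ANCOVA model, similar to the primary analysis". That model contains treatment, subgroup and their interaction, "with baseline score (not for analysis by baseline stage), CAP score, CAG repeat length (not for analysis by CAG repeat length"). The outcome is the change from baseline in whichever variable is of interest, so the exclusion of the baseline score in the stage analysis applies to every endpoint, not only to TFC. No reason is given for either exclusion.

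The primary ANCOVA in Section 6.6.2 keeps both: "The model will include the corresponding endpoint baseline score, CAG repeat length, baseline CAP score (defined in Section 4.1.1), and treatment as covariates".

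Two definitions elsewhere bear on the point. Section 1.1 says of stage: "The five clinical stages are defined by the score on the UHDRS Total Functional Capacity (TFC) Scale", with Stage 1 at 11–13, Stage 2 at 7–10 and Stage 3 at 3–6. Section 4.5.9.1 describes the cUHDRS as an "equally weighted sum of Z scores of the TFC, the TMS, the SDMT, and the SWR scores", so TFC is one part of four.

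**The concern.** A grouped factor is a coarse version of the variable it was cut from, and it says less still about other variables. Dropping the continuous covariate when the factor enters discards whatever that covariate predicts inside the groups.

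For TFC by stage, the loss is the spread of TFC within 11–13, 7–10 or 3–6. For the CAG analysis, it is the spread of CAG length on either side of 43, less what CAP still carries. For cUHDRS, TMS, SDMT or SWR by stage the loss is larger in kind, because stage was never a grouping of those baselines.

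If the dropped covariate predicts change, two things follow. The within-subgroup treatment effects and the interaction have wider intervals than the data allow. A chance imbalance in that covariate between arms within a subgroup also goes uncorrected, which matters most in small groups. Stage III, which the protocol would analyse only if enough patients are available, is the obvious case.

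**Working it through.** **The plan's own figure.** The protocol states no precision or power for subgroups. Its nearest figure is about 80% power with 267 per arm (Section 6.2). Rerunning the simulation described there, with 4,000 replicates, gave 79.5% (Monte Carlo standard error 0.6 points). The stated detectable difference of about 0.38 also reproduces, using 80% and 85% of 267 observed: 2.2414 × 1.78 × √(1/213.6 + 1/226.95) = 0.380. Neither figure uses the subgroup model, so neither is affected.

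**Formula.** Let r be the partial correlation of the dropped covariate with the change, given the covariates that stay. Let f be the share of that covariate's remaining variance that is left once the subgroup factor is fitted. Residual variance is proportional to 1 − r² with the covariate and to 1 − r² + r²f without it, so

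SE ratio = √(1 + r²f/(1 − r²)).

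**Inputs.** The protocol gives neither r nor f. I assume r = 0.1 to 0.5 and take f from a simulated baseline population:
- Age is about 48 (SD 9.5), limited to 25–65. CAG length is about 43.7 (SD 2.8), falling with age. CAP is above 400, as in Section 4.1.1.
- TFC is centred at 10.5 or at 9.5 and limited to 5–13. This gives Stage I/II/III shares of about 50/48/2% or 31/62/7%.
- The other three cUHDRS components are moderately related to the same underlying severity.

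Resulting f: 0.27–0.28 for TFC given stage, 0.44–0.48 for cUHDRS given stage, and 0.75 for CAG given its group with CAP kept.

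**Results: increase in SE from the omission.**

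| Analysis | f | r = 0.1 | r = 0.3 | r = 0.5 |
|---|---|---|---|---|
| TFC by stage | 0.27–0.28 | 0.1% | 1.3–1.4% | 4.3–4.6% |
| cUHDRS by stage | 0.44–0.48 | 0.2% | 2.2–2.3% | 7.1–7.6% |
| CAG analysis, CAP kept | 0.75 | 0.4% | 3.6% | 11.7% |
| Outer bound | 1 | 0.5% | 4.8% | 15.5% |

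Worked case, cUHDRS by stage at r = 0.3 and f = 0.475: √(1 + 0.09 × 0.475/0.91) = √1.047 = 1.023. In effective sample size, r = 0.3 costs about 3% (TFC), 4–5% (cUHDRS) and 7% (CAG).

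The CAG row depends on the split. The assumed population puts 84% at 43 or above. If the groups were more even, f would be smaller; at f = 0.36 the three entries become 0.2%, 1.8% and 5.8%.

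**Feasibility.** With stage, its interaction with treatment, CAP, CAG and baseline TFC all in the model, the design matrix has full rank (9 of 9). The variance inflation factor is about 4 for TFC given stage and about 1.6 for CAG given its group. The factor and the continuous covariate can be fitted together.

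**Consistency within Section 6.6.4.** The age analysis (split at 45) keeps both CAP and CAG. By the formula in Section 4.1.1, Age = CAP/(CAG − 33.66), so those two covariates determine age. The protocol therefore already accepts a split beside continuous covariates carrying the same information.

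**The case against.** The strongest reply is that little is at stake. The model may or may not be run, it is exploratory, no error rate or decision hangs on it, and the main subgroup output is descriptive. The synopsis leaves even the primary model's final covariate list to the SAP, so this list may change too. All of that stands and limits the point to a minor improvement. It does not remove the point, because the exclusions are written rules rather than details left open.

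The second reply is that each exclusion is targeted: the covariate goes only where a categorised relative comes in. CAP, which contains CAG length, stays throughout, and continuous CAG stays in the stage model. This is fair for TFC by stage and for the CAG analysis, and f below 1 already allows for it. With TFC and stage both fitted, the stage main effect is also harder to read, although the treatment contrasts are not. The reply does not reach cUHDRS, TMS, SDMT or SWR by stage.

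A reader might infer that the subgroup model contradicts the primary one. It does not: the text promises only a similar model, and any model with a subgroup interaction differs from the primary.

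A reader might also infer that the subgroup estimates are biased. They are not: stage and CAG group are fixed before randomisation, so treatment remains independent of the omitted covariate within each group.

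**Conclusion.** The point holds as a small, avoidable loss of precision in an optional analysis. It is clearest for cUHDRS, TMS, SDMT and SWR by stage. For TFC by stage, and for CAG with CAP kept, only within-group variation is lost. There is no bias and no effect on primary power, sample size or alpha.

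Under assumed partial correlations of 0.1 to 0.5, standard errors are wider by about 0.2–8% (cUHDRS by stage), 0.1–5% (TFC by stage) and 0.4–12% (CAG analysis). At 0.3 the range is about 1–4%. Both r and f are assumptions. If the covariate does not predict change within subgroups, nothing is lost except the adjustment for chance imbalance.

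A reader might want to express this as several points of power within one stage. The documents do not support that. The only effect and SD they give (0.54, from 1.36 − 0.82, and 1.78) are for TFC, so they cannot be paired with an assumed variance share for cUHDRS. They give no stage sizes, and no within-stage test is planned.

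**What to change.** In Section 6.6.4, delete both parentheses. Every subgroup model then keeps the continuous baseline score of the analysed endpoint and continuous CAG repeat length, beside CAP, subgroup, treatment and the treatment-by-subgroup interaction. The SAP should carry the same list. If the sponsor prefers to keep an exclusion, the reason should be stated.

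The cost is one degree of freedom in each affected model and a two-phrase edit. No new data are needed, since both covariates are already collected for the primary analysis.
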